9.2.2. Analysis Populations

Unless otherwise specified, the efficacy, health outcomes, and safety analyses will be conducted on the mITT population, defined as all randomized patients who received at least one dose of investigational product, even if the patient does not receive the correct treatment, or otherwise does not follow the protocol. Patients will be analyzed according to the treatment to which they were assigned. Significant protocol violations will be described in the SAP.

Safety analyses for the post-treatment Follow-up Period will be conducted on the follow-up population, defined as all randomized patients who received at least 1 dose of investigational product and have entered the post-treatment Follow-Up Period. Patients will be analyzed according to the dosing regimen to which they were assigned in the Treatment Period.

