6.2. Method of Treatment Assignment

Patients who meet all criteria for enrollment will be randomized in a 1:1:1 ratio (baricitinib 4-mg; baricitinib 2-mg; placebo) to double-blind treatment at Visit 2 (Week 0). Randomization will be stratified by disease activity (SLEDAI-2K <10; SLEDAI-2K ≥10), anti-dsDNA status (positive; negative), and region (defined in the SAP). Assignment to treatment groups will be determined by a computer-generated random sequence using an interactive web-response system (IWRS). The IWRS will be used to assign 2 bottles (Bottle A and Bottle B), each containing 36 double-blind investigational product tablets to each patient, starting at Visit 2 (Week 0), and at each visit through Visit 8 (Week 20). Site personnel will confirm that they have located the correct bottles by entering a confirmation number found on the bottles into the IWRS. Patients will be instructed to take 1 tablet from Bottle A and 1 tablet from Bottle B each day.

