9.5. Safety Analyses

All safety data will be descriptively summarized by treatment groups and analyzed based on the mITT population. The safety analyses include AEs, laboratory analytes, QIDS-SR₁₆, and vital signs. The duration of dosing exposure will also be summarized. For the Double-Blinded Treatment period, the safety data will be summarized and analyzed with pairwise comparisons between each baricitinib dose and placebo. For the post-treatment Follow-Up Period, safety data will be summarized according to the dosing regimen to which they were assigned during the

treatment period. The categorical safety measures will be summarized with incidence rates and analyzed by Fisher exact test. The mean change in the continuous safety measures of the vital signs, QIDS-SR₁₆, physical characteristics, and laboratory values will be summarized by visits and analyzed by ANCOVA with treatment and baseline values in the model. Other continuous safety variables will be analyzed by t-tests, unless otherwise stated. Missing values will be imputed by modified last observation carried forward (mLOCF) for continuous vital signs and QIDS-SR₁₆ safety variables.

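### Safety data are grouped by assigned treatment even for patients who took the wrong product, so events on baricitinib in a placebo-assigned patient count under placebo, and the reverse

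*Protocol*

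**What the plan says.** Protocol Section 9.2.2 sets the default that "the efficacy, health outcomes, and safety analyses will be conducted on the mITT population". That population is every randomised patient who took at least one dose, "even if the patient does not receive the correct treatment, or otherwise does not follow the protocol". The grouping rule follows: "Patients will be analyzed according to the treatment to which they were assigned". For the post-treatment follow-up population, which is used for safety only, the rule is the same: "Patients will be analyzed according to the dosing regimen to which they were assigned in the Treatment Period".

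Section 9.5 repeats the choice: "All safety data will be descriptively summarized by treatment groups and analyzed based on the mITT population". For the double-blind period, "the safety data will be summarized and analyzed with pairwise comparisons between each baricitinib dose and placebo". Section 9.2.1 names the Fisher exact test for adverse events and other categorical safety data.

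The protocol defines no safety population by treatment received and makes no exception for patients who took a wrong product. Section 9.2.2 opens with a general qualifier that allows departures, but nothing in the protocol uses it for this purpose.

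**The concern.** Grouping by assignment protects the randomised comparison, and for efficacy any resulting dilution is conservative. For harm, dilution is not conservative. If a placebo-assigned patient takes active drug and has a drug-related event, the placebo rate rises and the difference shrinks. If a baricitinib-assigned patient takes placebo, an event-free course lowers the baricitinib rate.

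The rule is stated, not left open: the definition foresees that some patients will receive the wrong treatment and says where their data go. The packaging makes a wrong bottle matter, because each regimen in Table JAHH.2 is one tablet from Bottle A plus one from Bottle B, and Section 6.2 has both bottles assigned at every dispensing visit. Routine drug levels would not reveal active drug in a placebo-assigned patient, since Section 8.5 says placebo samples are not assayed. Detection therefore rests on dispensing and compliance records.

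At stake is the attribution of a few events. That matters most for uncommon ones, such as the severe or opportunistic infections and blood-count events named in Section 8.2.2, where 100 patients per arm may yield only a handful.

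**Working it through.** **The plan's own figure.** The protocol gives no number for misdosing or for its effect. The one related calculation, power in Section 9.1 (100 per arm, 40% versus 60%, two-sided 5%, chi-square without continuity correction), reproduces at 81.2% against the stated 81%. It concerns efficacy and does not change.

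**Opportunity for error.** Two bottles at each of Visits 2 to 8 is 2 × 7 = 14 bottles per patient, and 14 × 300 = 4,200 at most. This counts bottles; it is not an error rate.

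**What a single wrong bottle does** (from Table JAHH.2 and Section 6.4):

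| Assigned | Wrong bottle | Regimen actually taken | Comparison with placebo, analysed by assignment |
|---|---|---|---|
| Placebo | A active | 4-mg | diluted |
| Placebo | B active | 2-mg | diluted |
| 4-mg | A placebo | placebo | diluted |
| 2-mg | B placebo | placebo | diluted |
| 4-mg | B active | both active, off-regimen | not diluted |
| 2-mg | A active | both active, off-regimen | not diluted |

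The last column assumes that baricitinib raises the event rate. In the last two rows the patient takes more drug and stays in a baricitinib arm. If events rise with dose, that arm moves away from placebo.

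**Average effect.** Let pB and pP be the event risks on baricitinib and placebo, and let k of 100 placebo-assigned patients take baricitinib for the whole period (k is assumed).

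- One way: observed difference = pB − [(100 − k)·pP + k·pB]/100 = (1 − k/100)·(pB − pP).
- Swap of k patients in each direction: observed difference = (1 − 2k/100)·(pB − pP).

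| k | Loss, one way | Loss, two-way swap |
|---|---|---|
| 0 | 0% | 0% |
| 1 | 1% | 2% |
| 2 | 2% | 4% |
| 5 | 5% | 10% |
| 10 | 10% | 20% |

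For example, with pB = 5%, pP = 1% and k = 1 one way, the difference falls from 4.00 to 3.96 points. These figures assume wrong product throughout. A one-bottle error usually spans about 4 of 24 weeks. If events accrue evenly and follow the product being taken, the one-way loss for k = 1 is about 1% × 4/24 = 0.17%.

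**A single rare event.** Assume one placebo-assigned patient took baricitinib and had the event. Moving that patient to the baricitinib arm changes the Fisher exact result as follows (all counts assumed):

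| By assignment | p | By treatment received | p |
|---|---|---|---|
| 5/100 v 1/100 | 0.21 | 6/101 v 0/99 | 0.029 |
| 4/100 v 1/100 | 0.37 | 5/101 v 0/99 | 0.059 |
| 10/100 v 5/100 | 0.28 | 11/101 v 4/99 | 0.105 |

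The p-value falls in each row, but it crosses 0.05 only in the first. The crossing depends on the counts chosen.

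**The case against.** The strongest reply is that the rule bites only after an error that the protocol guards against. Section 6.2 has site staff enter a confirmation number from each bottle into the IWRS. Section 6.7 requires tablet counts at each treatment visit and recording of dosing deviations. Both points stand: 4,200 bottles do not show that errors are likely.

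A reader might infer that assigned-arm grouping always understates harm. It does not. The two both-active combinations raise exposure within a baricitinib arm and need not pull it toward placebo.

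A reader might also infer that every misdosed patient with an event moves two arms by a percentage point in opposite directions. That requires the event to belong to the wrong product. An event before a one-bottle error, or well after it was corrected, may be correctly placed already.

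Finally, a reader might infer that the rule hides harm in data meant to settle the dose. The protocol states no such purpose. Under Section 8.4.7 serious reports are reviewed individually, and those that are unexpected and possibly related are unblinded to the sponsor's safety group, whatever the tables show.

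The SAP is not at hand and could add a table or listing by treatment received. That softens the point but does not remove the protocol's stated default.

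**Conclusion.** The point holds as a minor one. Sections 9.2.2 and 9.5 fix assigned-treatment grouping for safety in both the treatment and follow-up periods, including for patients who took the wrong product. Events can therefore be counted under a treatment the patient was not taking.

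The size is zero without errors. With one to five fully misdosed placebo patients per 100, the loss is 1% to 5% of the risk difference one way, or 2% to 10% if equal numbers are swapped in both directions. It is less for a brief error. A single rare event can matter more to one comparison, but that illustration uses chosen counts and predicts nothing. All of this rests on an assumed number of misdosed patients. The direction is toward no difference for placebo/active swaps and is not fixed for other errors.

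**What to change.** Keep efficacy and health outcomes by assigned treatment. In Section 9.2.2 (both populations) and Section 9.5:

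- Group safety data by treatment actually received, defined as the regimen taken for most of the patient's treatment period. A brief one-bottle error then does not reclassify anyone.
- List every patient who took any wrong product or an off-regimen combination, with product dates and event onset dates. The majority rule leaves events during a brief error in the original arm, and the both-active combination fits none of the three regimens; the listing makes both visible.

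Classifying by the highest active regimen ever taken would be worse. One wrong bottle would move all of a placebo patient's events into a baricitinib arm, including those that preceded the error, and it too has no place for the both-active combination.

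The cost is a short rule, a derived variable and a listing, settled before unblinding. If no errors occur, the tables are identical. Otherwise safety and efficacy arm sizes may differ by a few patients, and those few leave their randomised group in the safety comparisons. Section 9.2 requires an amendment only when a principal feature changes. If the sponsor judges that this is not one, the change can be made in the SAP and explained in the study report.

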9.2.3. Baseline Definition

Baseline will be defined as the last available value before the first dose of investigational product for both efficacy and safety analyses. In most cases, this will be the measure recorded at Week 0 (Visit 2). Change from baseline will be calculated as the visit value of interest minus the baseline value. For the post-treatment Follow-up Period, the baseline is defined as the last nonmissing assessment on or prior to entering the post-treatment Follow-up Period, that is, on or prior to the Week 24 visit (Visit 9), or the end of treatment visit (including ETV).

9.2.4. Missing Data Imputation

The patients will be considered nonresponders for the NRI analysis if they do not meet the clinical response criteria (for example, remission of rash/arthritis, SRI-4) at Week 24. All nonresponders at Week 24 as well as all patients who discontinue study treatment at any time prior to Week 24, for any reason, will be defined as nonresponders for the NRI analysis for all categorical analyses at Week 24. Patients who require initiation or increase in dose of NSAIDs, corticosteroids, antimalarials, or immunosuppressants after randomization (as outlined in Section 6.8, Concomitant Therapy) will be analyzed as nonresponders from the day of initiation or increase in medication. Randomized patients without at least 1 postbaseline observation will also be defined as nonresponders for the NRI analysis. MMRM is the primary analysis method for analyzing the continuous efficacy endpoints. In this method no imputation is needed. However, a sensitivity analysis, the placebo multiple imputation (pMI) method will be used for

the selected analyses of the continuous endpoints at Visit 9 (Week 24). The pMI assumes that the statistical behavior of drug- and placebo-treated patients after discontinuing investigational product becomes that of placebo-treated patients.

9.2.5. Adjustment for Multiple Comparisons

No adjustment for multiple comparisons will be done.

9.2.6. Adverse Events/Laboratory Results of Special Interest

Adverse events or laboratory results of special interest include severe or opportunistic infections, myelosuppressive events of anemia, leukopenia, neutropenia, lymphopenia, thrombocytopenia, thrombocytosis; and elevations in ALT/AST (≥ 3 x ULN) and total bilirubin (≥ 2 x ULN). The number of AESIs as well as the percentage of patients who experienced at least 1 AESI will be summarized by treatment group.

9.3. Treatment Group Comparability

9.3.1. Patient Disposition

A detailed description of patient disposition by treatment will be summarized with reasons for discontinuation.

9.3.2. Patient Characteristics

Summary tables by treatment group will be generated for demographics and patient characteristics at baseline (Visit 2), for historic diagnoses, and for preexisting conditions.

9.3.3. Concomitant Therapy

Concomitant therapy will be summarized and reported for the Double-Blinded Treatment Period. A listing of patients using excluded medications during the period will be provided.

9.3.4. Treatment Compliance

Compliance to therapy will be reported for the Double-Blinded Treatment Period as described in Section 6.7.

9.4. Primary and Secondary Analyses

9.4.1. Primary Analyses

The primary endpoint is the proportion of patients who achieve remission of arthritis and/or rash as defined by the SLEDAI-2K at Week 24. Either arthritis or rash (as defined by the SLEDAI-2K) are required to be present at baseline. If only arthritis is present at baseline, then arthritis has to be absent at Week 24 to meet the primary endpoint. If only rash is present at baseline, then rash has to be absent at Week 24 to meet the primary endpoint. If both arthritis and rash are present at baseline, then the primary endpoint is met if either arthritis, or rash, or both arthritis and rash are absent at Week 24.

Treatment comparison between baricitinib dose regimens (4-mg or 2-mg) and placebo in the proportion of patients achieving remission of arthritis and/or rash at Week 24 (Visit 9) will be analyzed using the logistic regression analysis with treatment and baseline disease activity (SLEDAI-2K <10 versus SLEDAI-2K \geq 10), baseline anti-dsDNA status (positive; negative), and region in the model. The proportions and 95% CI will be reported. Missing data will be imputed using the NRI method.

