4.3. Scientific Rationale for Study Design

The scientific rationale for the primary endpoint of this study is based on analyses from 2 large tabalumab SLE Phase 3 trials with a similar patient population involving over 2200 patients (Isenberg et al. 2015; Merrill et al. 2015). The primary endpoint in these trials was SRI-5. The goal of these analyses was to characterize the clinical symptoms most responsible for achieving responder status with SRI-5, and then use this information to design a more efficient trial with clinically relevant endpoints.

To achieve SRI-5, one needs improvement in SLEDAI, with no worsening in BILAG or Physician's Global Assessment of Disease Activity. In the Phase 3 trials, BILAG and Physician's Global Assessment of Disease Activity contributed minimal information to SRI-5, as fewer than 1% of patients achieved a ≥ 5 -point reduction in SLEDAI score, but failed the endpoint due to worsening of BILAG or Physician's Global Assessment of Disease Activity. These data provided the rationale to focus on SLEDAI as the primary driver of clinical response.

The SLEDAI is a weighted disease activity index that measures presence or absence of disease in 9 organ systems. Disease activity in the mucocutaneous, musculoskeletal, or immunologic organ systems was present in over 70% of patients at baseline, with over 98% of patients having mucocutaneous and/or musculoskeletal disease at baseline. In contrast, in the other 6 organ systems these diseases were present in $\leq 15\%$ of patients. These data provided the rationale to focus on mucocutaneous and musculoskeletal disease as the primary driver of clinical response.

The 9 SLEDAI organ systems are composed of specific disease symptoms. The musculoskeletal organ system consists of arthritis and myositis. Arthritis was the most prevalent symptom at baseline ($>80\%$ of patients) while myositis was rare ($\sim 1\%$ of patients). The mucocutaneous organ system includes rash, alopecia, and mucosal ulcer. Rash was the most common symptom in this organ system ($\sim 70\%$ of patients), followed by alopecia ($\sim 55\%$) and mucosal ulcer ($\sim 30\%$). These data, in consultation with SLE experts, provided the rationale to focus on remission of arthritis and rash as the primary endpoint in the clinical trial.

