9.1. Determination of Sample Size

Approximately 300 patients will be randomized in a 1:1:1 ratio to the baricitinib 4-mg, 2-mg, and placebo treatment groups. With 100 patients per treatment group, this study will have approximately 81% power to detect a difference between baricitinib 4-mg or 2-mg and placebo of $\geq 20\%$ in remission rates of rash and/or arthritis at Week 24. The sample size was determined based on the chi-square test with 2-sided type I error of 5% and 40% remission rate of rash and/or arthritis in placebo treatment group. The sample size calculation was performed using nQuery® Advisor 7.0 software.

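### The primary logistic model omits baseline manifestation (arthritis only, rash only, both), a probably prognostic factor that is already collected and not stratified: a minor loss of precision

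*Protocol*

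**What the plan says.** Protocol Section 9.4.1 makes response depend on what was present at baseline.

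- One manifestation: "If only arthritis is present at baseline, then arthritis has to be absent at Week 24 to meet the primary endpoint". The rule for rash only is the mirror image.
- Both: "If both arthritis and rash are present at baseline, then the primary endpoint is met if either arthritis, or rash", or both together, are absent at Week 24.

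The same section analyses this endpoint by "logistic regression analysis with treatment and baseline disease activity" (SLEDAI-2K below 10 versus 10 or more), plus anti-dsDNA status and region. It reports proportions with a 95% CI and imputes missing data as nonresponse. Section 9.2.1 repeats the covariate list. Section 6.2 uses the same three factors for allocation: "Randomization will be stratified by disease activity (SLEDAI-2K <10; SLEDAI-2K ≥10), anti-dsDNA status (positive; negative), and region (defined in the SAP"). The optional subgroups in Section 9.7.2 do not name manifestation.

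The data are there. Appendix 2 schedules the SLEDAI-2K at Visit 2, and the endpoint cannot be scored without classifying each patient as arthritis only, rash only or both.

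**The concern.** A patient with both manifestations responds if either clears; a patient with one responds only if that one clears. Unless patients with both clear each manifestation correspondingly less often, they respond more often. The variable that defines the response rule is then a predictor of response that is neither balanced by design nor adjusted for.

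Two things are at stake, both modest. The comparison may lose a little precision that existing data could supply. And a chance difference between arms in the share with both manifestations would move the estimated remission difference uncorrected. Because both doses are compared with one placebo arm, an unusual placebo mix would move both estimates in the same direction.

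**Working it through.** **1. The plan's own power.** Inputs from Section 9.1: 100 per arm, placebo 40%, difference 20 points, two-sided 5%, chi-square test.

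- Standard error under the null: √(2 × 0.50 × 0.50 / 100) = 0.0707
- Standard error under the alternative: √((0.40 × 0.60 + 0.60 × 0.40) / 100) = 0.0693
- Power = Φ((0.20 − 1.96 × 0.0707) / 0.0693) = Φ(0.886) = 81.2%

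This reproduces the stated figure.

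**2. Baseline mix (assumption).** Section 4.3 gives arthritis in more than 80% and rash in about 70% of patients in two earlier Phase 3 trials.

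- If the two are independent: 0.56 / 0.94 = 60% of eligible patients have both.
- If 98% have at least one (borrowed from that section's figure for any mucocutaneous or musculoskeletal disease): (0.80 + 0.70 − 0.98) / 0.98 = 53% have both, 29% arthritis only, 18% rash only.

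The simulation in step 4 used 28%/18%/54%.

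**3. Size of the gap (assumption).** Let q be the remission probability per manifestation, equal in all patients, and φ the within-patient correlation between the two remissions. The gap in response between patients with both and patients with one is q(1 − q)(1 − φ). Solving for q at overall rates of 40% and 60%, with 53% having both:

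| φ | Placebo, one vs both | Active, one vs both | Mean gap |
|---|---|---|---|
| 0 | 29.1% vs 49.7% | 46.8% vs 71.7% | 22.8 points |
| 0.3 | 31.9% vs 47.2% | 50.7% vs 68.2% | 16.4 points |
| 0.5 | 34.0% vs 45.3% | 53.4% vs 65.8% | 11.8 points |

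With w the share having both, the fraction of variance removed is 2w(1 − w) × gap² / 0.48. For φ = 0 this is 2 × 0.53 × 0.47 × 0.2275² / 0.48 = 5.4%. Across w of 0.50-0.60 and φ of 0-0.5 the range is 1.4-5.5%, and power becomes 81.8-83.4%. This calculation ignores the SLEDAI-2K term already planned, so it leans high.

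**4. With a SLEDAI-2K ≥10 term already in the model.** Simulation of 4,000 trials per scenario, 100 per arm, assuming SLEDAI-2K ≥10 in 70% of patients with both and 30% of the others. Power is converted from the mean test statistic in step 1: 0.886 + 1.960 = 2.846. For the first row, 2.846 × 1.021 = 2.906 and Φ(2.906 − 1.960) = 82.8%.

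| Scenario | Change in mean z | Implied power (from 81.2%) |
|---|---|---|
| Independent remissions | +2.1% | 82.8% |
| φ = 0.3 | +0.9% | 81.9% |
| φ = 0.5 | +0.5% | 81.6% |
| φ = 0.3, each manifestation clears 20% less often in patients with both | +0.1% | 81.3% |
| φ = 0.3, 30% less often | −0.1% | 81.1% |

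A separate simulation (6,000 trials, 60% with both, independent remissions, same 70%/30% link) gave 80.9% without the term and 82.9% with it. With no link to SLEDAI-2K, type I error was 5.6% with and without the term.

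**5. Chance imbalance.** The standard deviation of the between-arm difference in the share with both is √(2 × 0.54 × 0.46 / 100) = 0.0705, so the 95% range is ±1.96 × 0.0705 = ±14 points. Multiplied by the mean gaps in step 3: 0.138 × 0.118 = 1.6 points to 0.138 × 0.2275 = 3.1 points. If the gap is nil, so is the shift.

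**The case against.** The strongest reply is that nothing here is invalid. The model carries exactly the three stratification factors, which is conventional, and randomization protects the test. Chance imbalance is not bias, and its variability is already in the standard error and the planned power. All of that stands.

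A reader might infer that patients with both manifestations must respond more often because they have two routes. The rule does not guarantee it. For placebo patients with both to respond at only 40%, the same as patients with one, each manifestation would have to clear in about 22.5% of them if remissions are independent (1 − √0.60), or about 30% if φ = 0.5, against 40% in patients with one. That is a 26-44% relative reduction. It is possible in more extensive disease, and the protocol has no data to exclude it. Section 9.2.4 also makes any discontinuation or SLE-medication increase a nonresponse, which fails both routes together and pushes the remissions towards positive correlation. The gain is therefore likely, not certain.

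A reader might also expect the covariate to narrow the confidence interval of the odds ratio. It does not. In the independent-remission scenario the standard error of the log odds ratio rose from 0.292 to 0.306; the test gains because the conditional odds ratio is larger. Nor does the covariate alone alter the observed proportions that Section 9.4.1 reports, or their difference.

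Finally, the SAP could add the factor. The protocol, however, writes out the covariate list for the primary model, so the point concerns what it states.

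**Conclusion.** The point holds as a minor improvement. Baseline manifestation is absent from the primary model and from stratification, is already recorded, and is probably prognostic because of the endpoint rule. The benefit of adjusting is about 0-2% in the mean test statistic and about 0-2 points of power. It is largest with independent remissions, and about nil when remissions are correlated and patients with both clear each manifestation 20-30% less often. No scenario showed a material loss. The imbalance that adjustment would remove is up to about 1.5-3 points on a planned 20.

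These sizes rest on an assumed baseline mix, assumed remission rates by manifestation and an assumed link to SLEDAI-2K. The protocol supplies only the prevalence figures, the overall placebo rate and the target difference. A reader might infer that the primary analysis is biased or underpowered; the documents do not support that, since the test is valid and the 81% reproduces.

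**What to change.** Add baseline manifestation (arthritis only, rash only, both) as a three-level factor to the primary logistic model in Section 9.4.1 and to the Week 12 version of the endpoint in Table JAHH.4. Report a covariate-standardized risk difference with 95% CI next to the observed proportions, so that the adjustment reaches the reported difference. Prespecify both before unblinding, which avoids a post hoc adjustment if an imbalance appears.

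The cost is two degrees of freedom and an odds ratio that is conditional on manifestation, which should be said where it is reported. No new data, patients or change to the sample size are needed.
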